2.0 OBJECTIVES

2.1 Primary Objective

To determine the progression-free survival (PFS) with irinotecan plus ramucirumab in patients with metastatic gastric and gastro-esophageal junction cancer who have progressed after first line chemotherapy.

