10.0 STUDY CALENDAR

Screening/baseline evaluations are to be conducted within 28 days prior to start of protocol therapy. Cycles are 14 days long but may be extended to up to 21 days at physician discretion.

	Screening	Day 1 of each cycle (±/- 3 days)	Every 8 weeks (+/- 3 days	EOT (+/- 3 days)	F/U ¹
Informed consent	X				
Demographics and medical history	X				
ECOG PS, Vitals, weight	X	X			
Height	X			X	
Physical exam	X	X		X	X^5
EKG	X X				
CBC	X	X		X	
CMP	X	X		X	
PTT/INR	X				
Urinalysis or Urine Dipstick ⁶	X	X		X	
β-hCG ²	X				
Imaging ³ and RECIST 1.1 time point response	X		X	X^4	
Ramucirumab		X			
Irinotecan		X			
Tumor Biopsy (Wash U only)	X^7				
Blood for angiome profiling			nt on C1D1, C5D1, . C9D1	X	
Blood for cfDNA			nt on C1D1, C3D1, D1, and C9D1	X	
Collection of HER2 status	At some point during the study				
Adverse event assessment	X			X	X
Survival information					X

- 1. 30 days after EOT visit, then every 2 months. AEs only collected for 30 days after treatment discontinuation.
- 2. Women of childbearing potential only
- 3. Imaging (CT or MRI) will be performed every 8 weeks, +/- 7days, regardless of dosing/cycle delays up to 1 year. After 1 year, the imaging frequency is at the discretion of the treating physician. Information from lesion evaluation by imaging done as part of routine care will be collected until progressive disease has been objectively determined if the patient discontinued treatment due to any other reason than progressive disease.
- 4. EOT imaging not required if most recent scan has been performed within 21 days prior to EOT.
- 5. Physical exam will only be done if the follow-up visit involves an in-person office visit.
- 6. A urine dipstick may be performed in lieu of a full urinalysis, however, if the dipstick is abnormal, confirm urine protein with a full urinalysis. If urinalysis or dipstick shows protein ≥ 2+, a 24-hour urine collection must be collected.
- 7. If safe and feasible, biopsies are to be performed at least 7 days prior to the planned C1D1. See Section 9.1 for additional information.

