12.3 Methods for Evaluation of Measurable Disease

All measurements should be taken and recorded in metric notation using a ruler or calipers. All baseline evaluations should be performed as closely as possible to the beginning of treatment and never more than 4 weeks before the beginning of the treatment.

The same method of assessment and the same technique should be used to characterize each identified and reported lesion at baseline and during follow-up. Imaging-based evaluation is preferred to evaluation by clinical examination unless the lesion(s) being followed cannot be imaged but are assessable by clinical exam.

Clinical lesions: Clinical lesions will only be considered measurable when they are superficial (e.g., skin nodules and palpable lymph nodes) and ≥10 mm diameter as assessed using calipers (e.g., skin nodules). In the case of skin lesions, documentation by color photography, including a ruler to estimate the size of the lesion, is recommended.

Chest x-ray: Lesions on chest x-ray are acceptable as measurable lesions when they are clearly defined and surrounded by aerated lung. However, CT is preferable.

Conventional CT and MRI: This guideline has defined measurability of lesions on CT scan based on the assumption that CT slice thickness is 5 mm or less. If CT scans have slice thickness greater than 5 mm, the minimum size for a measurable lesion should be twice the slice thickness. MRI is also acceptable in certain situations (e.g. for body scans).

Use of MRI remains a complex issue. MRI has excellent contrast, spatial, and temporal resolution; however, there are many image acquisition variables involved in MRI, which greatly impact image quality, lesion conspicuity, and measurement. Furthermore, the availability of MRI is variable globally. As with CT, if an MRI is performed, the technical specifications of the scanning sequences used should be optimized for the evaluation of the type and site of disease. Furthermore, as with CT, the modality used at follow-up should be the same as was used at baseline and the lesions should be measured/assessed on the same pulse sequence. It is beyond the scope of the RECIST guidelines to prescribe specific MRI pulse sequence parameters for all scanners, body parts, and diseases. Ideally, the same type of scanner should be used and the image acquisition protocol should be followed as closely as possible to prior scans. Body scans should be performed with breath-hold scanning techniques, if possible.

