12.4.3 Evaluation of Best Overall Response

The best overall response is the best response recorded from the start of the treatment until disease progression/recurrence (taking as reference for progressive disease the smallest measurements recorded since the treatment started). The patient's best response assignment will depend on the achievement of both measurement and confirmation criteria.

For Patients with Measurable Disease (i.e., Target Disease)

For Tatients with Measurable Disease (i.e., Target Disease)				
Target	Non-Target	New	Overall	Best Overall Response
Lesions	Lesions	Lesions	Response	when Confirmation is
			_	Required*
CR	CR	No	CR	>4 wks. Confirmation**
CR	Non-CR/Non-	No	PR	
	PD			
CR	Not evaluated	No	PR	>4 wks. Confirmation**
PR	Non-CR/Non-	No	PR	24 wks. Commination .
	PD/not			
	evaluated			
SD	Non-CR/Non-	No	SD	Documented at least once
	PD/not			>4 wks. from baseline**
	evaluated			24 WKS. Holli baselille
PD	Any	Yes or	PD	
		No		
Any	PD***	Yes or	PD	no prior SD, PR or CR
		No		
Any	Any	Yes	PD	

^{*} See RECIST 1.1 manuscript for further details on what is evidence of a new lesion.

Note: Patients with a global deterioration of health status requiring discontinuation of treatment without objective evidence of disease progression at that time should be reported as "symptomatic deterioration." Every effort should be made to document the objective progression even after discontinuation of treatment.

^{**} Only for non-randomized trials with response as primary endpoint.

^{***} In exceptional circumstances, unequivocal progression in non-target lesions may be accepted as disease progression.

For Patients with Non-Measurable Disease (i.e., Non-Target Disease)

Non-Target Lesions	New Lesions	Overall Response
CR	No	CR
Non-CR/non-PD	No	Non-CR/non-PD*
Not all evaluated	No	not evaluated
Unequivocal PD	Yes or No	PD
Any	Yes	PD

^{* &#}x27;Non-CR/non-PD' is preferred over 'stable disease' for non-target disease since SD is increasingly used as an endpoint for assessment of efficacy in some trials so to assign this category when no lesions can be measured is not advised

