12.4.4 Duration of Response

Duration of overall response: The duration of overall response is measured from the time measurement criteria are met for CR or PR (whichever is first recorded) until the first date that recurrent or progressive disease is objectively documented (taking as reference for progressive disease the smallest measurements recorded since the treatment started).

The duration of overall CR is measured from the time measurement criteria are first met for CR until the first date that progressive disease is objectively documented.

Duration of stable disease: Stable disease is measured from the start of the treatment until the criteria for progression are met, taking as reference the smallest measurements recorded since the treatment started, including the baseline measurements.

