15.3 Secondary Efficacy Measures

- Overall Survival Time (OS):
 - OS time will be measured from date of study entry to date of death from any cause. For those who are alive, we censor them at the time of loss to follow-up (very few) or at 30 months from the date of treatment discontinuation, which come first.
- Time to Progressive Disease (TTP):
 - TTP is defined as the time from study entry until date of radiographic PD using RECIST v1.1 criteria. For those who are alive and do not experience progression, we censor them at the time of loss to follow-up (very few) or at 12 months from the study entry, which come first. For those who are dead before progression, we will consider death as the competing risk. If the number of death are very small, we will censor them at time of death.
- Best Overall Response (BOR) of Complete Response (CR), Partial Response (PR), Stable Disease (SD) or PD:
 - BOR is defined as the best response across all time points from randomization until radiologically confirmed PD using RECIST, v1.1 criteria. CR is defined as the disappearance of all target and non-target lesions and any pathological lymph nodes (whether target or non-target) must have reduction in short axis to <10 mm and normalization of tumor marker level of non-target lesions. PR is defined as having a \geq 30% decrease in sum of longest diameter (LD) of target lesions. PD was defined as having a \geq 20% increase in sum of LD of target lesions and \geq 5 mm increase above nadir. SD was defined as small changes that did not meet above criteria.
- Objective Response Rate (ORR):
 ORR is defined as the percentage of participants with confirmed CR or confirmed PR.
- Clinical Benefit Rate (CBR):
 CBR is defined as percentage of combined patients who have achieved confirmed CR,
 PR and SD.

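### The plan sets no effective minimum time on treatment for stable disease, so an early end-of-treatment scan without progression can count as clinical benefit

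*Combined protocol and SAP*

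**What the plan says.** - **Minimum interval for SD.** The best-response table in Section 12.4.3 asks that SD be documented at least once, ">4 wks. from baseline". The cell carries a double asterisk, explained below the table as "Only for non-randomized trials with response as primary endpoint". The SD definitions in 12.4.1 and 15.3 have no time requirement.
- **Primary endpoint.** Section 2.1: "To determine the progression-free survival (PFS) with irinotecan plus ramucirumab". Response is secondary.
- **Baseline window.** Section 12.3 wants baseline evaluations close to the start of treatment and "never more than 4 weeks before the beginning of the treatment". Section 10.0 agrees: "Screening/baseline evaluations are to be conducted within 28 days prior to start of protocol therapy".
- **EOT scan.** Section 10.0, footnote 4: "EOT imaging not required if most recent scan has been performed within 21 days prior to EOT".
- **Scheduled imaging.** Every 8 weeks. The Section 10.0 column header allows 3 days either side; footnote 3 allows 7.
- **Evaluability.** Under Section 5.3 a patient is excluded from response only if treatment stops before Cycle 4 is complete and there has been no disease assessment.
- **CBR.** Section 15.3: "CBR is defined as percentage of combined patients who have achieved confirmed CR", followed by PR and SD. Section 2.2 attaches confirmation to CR and to PR, not to SD. Neither section gives a minimum SD duration or a denominator.
- **Duration of SD.** Section 12.4.4: "Stable disease is measured from the start of the treatment until the criteria for progression are met".

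**The concern.** SD is what an early scan shows by default when the tumour has had little time to change. A disease-control endpoint therefore needs a minimum time on treatment before SD counts. Here a patient who stops after one dose, for toxicity for example, can be scanned at EOT, show no progression, and enter the CBR numerator well before the first scheduled restaging. The error runs one way: such patients can only raise CBR. In a single-arm trial no control arm is inflated alongside, so a reader comparing the CBR with other studies has no internal check.

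**Working it through.** **1. The plan's own figure.** The documents state no CBR value. The only related figure is N = 40, used below as the denominator. Section 15.1 inputs: median PFS 4 versus 2.5 months, exponential, one-sided 0.05, one-sample log-rank, 12 months of accrual plus 12 of follow-up.

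- Per patient under the alternative: observed event probability p1 = 0.947; expected events at the null hazard p0 = 0.947 × 4/2.5 = 1.516; difference 0.568; standard deviation of the difference 1.470.
- Power = Φ[(√40 × 0.568 − 1.645 × √1.516)/1.470] = Φ[(3.595 − 2.025)/1.470] = Φ(1.068) = 85.7%.

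The stated 85% is reproduced (39 patients suffice in this form). Nothing below changes it.

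**2. If the 4-week rule applies.** Let b be the days from baseline scan to first dose (0 to 28). A scan d days after first dose is b + d days from baseline, so the earliest qualifying scan is d = 28 − b, or 29 − b if the inequality is strict. The EOT scan is no longer waived once b + d exceeds 21, that is from d = 22 − b.

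| b (days) | Earliest SD, at least 28 days | Earliest SD, more than 28 days | EOT scan called for from |
|---|---|---|---|
| 28 | day 0 | day 1 | any time after dosing |
| 21 | day 7 | day 8 | day 1 |
| 14 | day 14 | day 15 | day 8 |
| 7 | day 21 | day 22 | day 15 |
| 0 | day 28 | day 29 | day 22 |

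A scan at least 28 days after baseline is always past the 21-day waiver, so if no scan has been done since baseline the calendar itself calls for it. Example: b = 27, one dose, EOT scan 7 days later. 27 + 7 = 34 days from baseline, so the rule is met after one week on treatment.

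**3. If the footnote switches the rule off.** The trial is non-randomized, but response is not its primary endpoint, so the footnote's condition fails. No other section sets a minimum, so any post-dose scan without progression can be SD.

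**4. Scheduled restaging, for comparison.** Eight weeks is day 56. The lower edge is 56 − 7 = day 49 (footnote 3) or 56 − 3 = day 53 (column header).

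**5. Effect on CBR.** With a fixed denominator of 40, k such patients add k/40: 1 adds 2.5 points, 2 add 5, 4 add 10. The denominator matters. Suppose, as an assumption, 20 other patients have clinical benefit and one early-scan patient is in question:

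- counted as benefit: 21/40 = 52.5%
- dropped as unevaluable: 20/39 = 51.3%
- kept in the denominator as no benefit: 20/40 = 50.0%

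**The case against.** **The footnote.** A reader might infer that timing SD from baseline is the whole fault and that moving the anchor to first dose cures it. The documents do not support that. If the footnote disapplies the rule, re-anchoring it changes nothing. In favour of the rule being in force, the plan does require confirmation of CR and PR (2.2, 12.1), from the same table column under the same footnote. But it never says so for SD. The gap exists on both readings and is wider on the literal one.

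**The extreme case.** If the 4-week rule applies, a qualifying scan within about a week of first dose needs a baseline 3 to 4 weeks before dosing, and Section 12.3 asks for baseline as close to treatment as possible. This stands as a limit on frequency; the window is still allowed.

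**The size.** It is tempting to suppose that 2 to 6 of 40 patients stop before week 7 without progression and to claim 5 to 15 points of inflation. No count in the documents supports this. It would also measure a 7-week threshold, not the baseline anchor: a patient scanned on days 29 to 48 passes a 4-week rule timed from first dose too.

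**Two clocks.** A reader might call 12.4.3 and 12.4.4 contradictory. Section 12.4.4 times how long SD lasts; the table cell sets when SD qualifies. These may have different origins. The mismatch is a reason to tidy, not an error in itself.

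**Chance of scan booking.** With b = 10 and a stop 7 days after dosing, the last scan is 17 days old and no EOT scan is required. One might infer that this patient is bound to be non-evaluable. Sections 10.0 and 12.1 collect later routine-care imaging until progression, so that need not follow.

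**Existing safeguards.** Section 12.4.3 reports global deterioration without objective progression as symptomatic deterioration. That flags one group of early stoppers, but not those who stop for toxicity, and it does not say how they enter CBR. CBR also has no test or threshold, which limits the consequence.

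**Conclusion.** The point holds: the plan has no effective minimum time on treatment for SD, whichever way the footnote is read. A patient handled exactly as the plan says can be recorded as having clinical benefit about a week after a single dose. The bias can only raise CBR, by 2.5 points per patient if the denominator is 40 treated patients. The denominator is an assumption because Section 15.3 does not state one. The total cannot be computed, because the documents give no expected number of early stoppers with a scan and no progression. The effect is confined to best response and CBR, both secondary; it does not touch the PFS analysis or its power. It is worth correcting because the remedy is cheap and works under both readings.

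**What to change.** 1. Replace the SD cell in the 12.4.3 table with one rule and repeat it in 15.3: SD counts toward best overall response and CBR only if documented at or after the first scheduled 8-week restaging (lower edge of its window), timed from start of treatment. Replace the 4-week wording outright, so that two minimums do not stand side by side.
2. Remove the double asterisk from that cell, so that the rule plainly applies in this trial.
3. Reconcile the 3-day and 7-day imaging windows in Section 10.0, since they set the lower edge (day 53 or day 49).
4. State in 15.3 that patients whose only scan is earlier and shows no progression are reported as not evaluable for best response, and stay in the CBR denominator as not having clinical benefit.

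Cost: a few sentences and no new scans. The downside is a slightly lower reported CBR.

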12.4.4 Duration of Response

Duration of overall response: The duration of overall response is measured from the time measurement criteria are met for CR or PR (whichever is first recorded) until the first date that recurrent or progressive disease is objectively documented (taking as reference for progressive disease the smallest measurements recorded since the treatment started).

The duration of overall CR is measured from the time measurement criteria are first met for CR until the first date that progressive disease is objectively documented.

Duration of stable disease: Stable disease is measured from the start of the treatment until the criteria for progression are met, taking as reference the smallest measurements recorded since the treatment started, including the baseline measurements.

12.4.5 Progression-Free Survival

PFS is defined as the duration of time from start of treatment to time of progression or death, whichever occurs first. For those who are alive and do not experience progression, we censor them at the time of loss to follow-up (very few) or at 12 months from the study entry, which come first.

12.4.6 Response Review

It is strongly recommended that all responses be reviewed by an expert(s) independent of the study at the study's completion. Simultaneous review of the patients' files and radiological images is the best approach.

13.0 DATA AND SAFETY MONITORING

In compliance with the Washington University Institutional Data and Safety Monitoring Plan, an independent Data and Safety Monitoring Board (DSMB) will be specifically convened for this trial to review toxicity data. A DSMB will consist of no fewer than 3 members including 2 clinical investigators and a biostatistician. DSMB members must be employed by Washington University, Barnes-Jewish Hospital, or St. Louis Children's Hospital. Like investigators, DSMB members are subject to the Washington University School of Medicine policies regarding standards of conduct. Individuals invited to serve on the DSMB will disclose any potential conflicts of interest to the trial principal investigator and/or appropriate university officials, in accordance with institution policies. Potential conflicts that develop during a trial or a member's tenure on a DSMB must also be disclosed.

Until such a time as the first secondary site enrolls its first patient, a semi-annual DSM report to be prepared by the study team will be submitted to the Quality Assurance and Safety Monitoring Committee (QASMC) semi-annually beginning 6 months after study activation at Washington University (if at least one patient has been enrolled) or one year after study activation (if no patients have been enrolled at the 6-month mark).

The DSM report for the DSMB will be prepared by the study team with assistance from the study statistician, will be reviewed by the DSMB, and will be submitted to the QASM Committee. The DSMB must meet beginning six months after enrollment of the first patient at a secondary site, no more than one month prior to the due date of the DSM report to QASMC. This report will include:

- HRPO protocol number, protocol title, Principal Investigator name, data coordinator name, regulatory coordinator name, and statistician
- Date of initial HRPO approval, date of most recent consent HRPO approval/revision, date of HRPO expiration, date of most recent QA audit, study status, and phase of study
- History of study including summary of substantive amendments; summary of accrual suspensions including start/stop dates and reason; and summary of protocol exceptions, error, or breach of confidentiality including start/stop dates and reason
- Study-wide target accrual and study-wide actual accrual including numbers from participating sites
- Protocol activation date at each participating site
- Average rate of accrual observed in year 1, year 2, and subsequent years at each participating site
- Expected accrual end date, accrual by site, and accrual by arm
- Objectives of protocol with supporting data and list the number of participants who have met each objective
- Measures of efficacy
- Early stopping rules with supporting data and list the number of participants who have met the early stopping rules
- Summary of toxicities at all participating sites and separated by arm
- Abstract submissions/publications
- Summary of any recent literature that may affect the safety or ethics of the study

Protocol Version: 10Jun2022 – Amendment 6 Page 48 of 64

Further DSMB responsibilities are described in the DSMB charter.

The study principal investigator and coordinator will monitor for serious toxicities on an ongoing basis. Once the principal investigator or coordinator becomes aware of an adverse event, the AE will be reported to the HRPO and QASMC according to institutional guidelines (Please refer to section 7.0).

Refer to the Washington University Quality Assurance and Data Safety Monitoring Committee Policies and Procedures for full details on the responsibilities of the DSMC at https://siteman.wustl.edu/research/clinical-research-resources/protocol-office-prmcqasmc/.

14.0 AUDITING

Since Washington University is the coordinating center, each site will be audited annually by Siteman Cancer Center personnel (QASMC) unless the outside institution has an auditing mechanism in place and can provide a report. The outside sites will be asked to send copies of all audit materials, including source documentation. The audit notification will be sent to the Washington University Research Patient Coordinator, who will obtain the audit materials from the participating institution.

Notification of an upcoming audit will be sent to the research team one month ahead of the audit. Once accrual numbers are confirmed, and approximately 30 days prior to the audit, a list of the cases selected for review (up to 10 for each site) will be sent to the research team. However, if during the audit the need arises to review cases not initially selected, the research team will be asked to provide the additional charts within two working days.

Additional details regarding the Auditing Policies and procedures can be found at http://www.siteman.wustl.edu/uploadedFiles/Research_Programs/Clinical_Research_Resources/Protocol_Review_and_Monitoring_Committee/QASMC%20Policies%20and%20Procedures%205-3-13.pdf

